Study Protocol and Statistical Analysis Plan

Musical Grammatological and Neurocognitive Parameterization of Analgesic and Anxiolytic
Effects of Culturally and Personally Contextualized Music Listening During Painful Dental
Procedures

16/07/2025

Musical Grammatological and Neurocognitive Parameterization of Analgesic and Anxiolytic Effects of Culturally and Personally Contextualized Music Listening During Painful Dental Procedures

I-Objective

This study aims to verify, with a significant sample of 30 Lebanese adults, the hypothesis that listening to a personally and culturally contextualized musical sequence during a painful dental procedure induces a significant decrease in perceived pain and patient anxiety. The music is chosen by the patient from a pre-established selection of tracks based on grammatological criteria recognized for their analgesic potential. The study also seeks to observe favorable modulation of physiological parameters related to stress.

II- Research Questions

- Can listening to a musical statement chosen from a pre-selected palette based on soothing musical grammatological criteria induce an analgesic effect in patients undergoing painful dental care?
- Would this musical statement have a modulating effect on the activity of the autonomic nervous system, particularly by inhibiting physiological responses associated with stress?
- Do the analgesic and anxiolytic effects of the musical sequence vary according to implicit cultural preferences (e.g., Mashriq musical tradition vs. Western music) expressed in the patient's choice?
- Are the musical sequences chosen freely by patients from a pre-established palette perceived as effective in mitigating pain and anxiety, and to what extent is this perception correlated with physiological data and self-assessments?

III- Musical Material

The patient is invited to choose a musical sequence from a palette of tracks from various musical genres, pre-selected for their relaxing and soothing musical grammatological criteria:

- Samā'ī in Rāst mode – Ghassan Sahhab
- Taḥmīlat Rāst – Album *Waṣalāt* – Nidaa Abou Mrad and the Antonine University Classical Arabic Music Ensemble
- Bašraf Rāst – Album *Waṣalāt* – Nidaa Abou Mrad and the Antonine University Classical Arabic Music Ensemble
- Bašraf Rāst – Album *Mikha'il Mashâqa* – Nidaa Abou Mrad and the Antonine University Classical Arabic Music Ensemble
- Taqṣīm in Rāst mode – Ghassan Sahhab
- "In a Sentimental Mood" in D Major – Duke Ellington

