4. **Baseline (Phase 0):** Heart rate (HR) and blood pressure (BP) are measured at rest (T0).
5. **Control 1 (Phase 1):** 30 seconds of drilling without music. Measurements: HR, BP, and Pain Intensity (PI) via Visual Analog Scale (T1).
6. **Pause/rest (120s) + beginning of the music listening**
7. **Test (Phase 2):** 30 seconds of drilling *during* music playback. Measurements: HR, BP, and PI (T2).
8. **End of the music listening - Pause/rest (120s)**
9. **Control 2 (Phase 3):** 30 seconds of drilling. Measurements: HR, BP, and PI (T3).
10. **Completion:** The patient completes a post-treatment evaluation questionnaire. Note: The study takes place at the start of the clinical visit; dental treatment continues normally after the final study measurements are taken.

VI- Statistical Analysis Plan (SAP)

VI-1 Study Design

- **Type:** Single-arm, within-subject experimental study.
- **Participants:** 30 adults undergoing dental treatment for caries.
- **Phases:** Baseline (T0), Phase 1 (pre-music silence), Phase 2 (music), Phase 3 (post-music silence).
- Each participant serves as their own control.

VI-2- Data Collection: Pain measured via Visual Analog Scale (VAS); heart rate (HR) and systolic/diastolic blood pressure (BP) recorded at all phases.

VI-3- Statistical Methods

Primary Outcome – Pain (VAS)

- **Analysis:**
 - Compare pain levels across phases using repeated measures ANOVA (or Friedman test if data violate normality).
 - Post-hoc pairwise comparisons between phases (Phase 1 vs Phase 2, Phase 2 vs Phase 3) using Bonferroni adjustment to correct for multiple testing.
- **Assumptions:**
 - Normality of residuals checked with Shapiro-Wilk test.
 - Sphericity checked with Mauchly's test; Greenhouse-Geisser correction applied if violated.

Secondary Outcomes

- **Physiological Parameters (HR, BP)**
- **Analysis:**
 - Repeated measures ANOVA for HR, systolic BP, and diastolic BP across the four phases.
 - Pairwise comparisons with Bonferroni correction.
- **Assumptions:** Same as primary outcome; log transformation applied if data are skewed.
- **Post-Treatment Perception of Music Effectiveness**
- **Analysis:**
 - Frequency distributions and descriptive statistics.
 - Association with pain reduction and physiological changes assessed using Spearman correlation.

VI-4- Software

- Statistical analyses will be performed using Python.

Bibliography

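### Single-step Bonferroni in VI-3 is valid but gives away power that Holm's step-down would keep; the gain depends on assumed effects, about 0 to 14 points for showing both pain contrasts and less for the stated hypothesis

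*Combined protocol and SAP*

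**What the plan says.** Section VI-1 describes a "Single-arm, within-subject experimental study", and section I sets the size at 30 adults, so every phase contrast is a paired comparison within the same patients. For pain, VI-3 first plans an overall test: "Compare pain levels across phases using repeated measures ANOVA (or Friedman test if data violate normality)". It then plans "Post-hoc pairwise comparisons between phases (Phase 1 vs Phase 2, Phase 2 vs Phase 3) using Bonferroni adjustment to correct for multiple testing", a family of two named contrasts.

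For HR, systolic BP and diastolic BP, VI-3 plans a repeated measures ANOVA over four phases and then "Pairwise comparisons with Bonferroni correction". It does not list the pairs. Four phases give up to six pairs per parameter.

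No step-down method is mentioned. Alpha, sidedness, target power, effect size, SD and correlation are not stated. The hypothesis in section I is that music "induces a significant decrease in perceived pain and patient anxiety". A return of pain after the music stops is not named as a condition of success.

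**The concern.** Bonferroni tests every pair in a family of m at alpha/m. Holm orders the p-values, tests the smallest at alpha/m, and relaxes the threshold after each rejection. Both control the family-wise error strongly with no assumption about dependence between the tests, but Holm never rejects less. For the tests themselves, the single-step version therefore gives up power and gets no extra error protection in return.

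This matters most for the second pain contrast. The order of conditions is fixed (no music, music, no music) and there is no concurrent control. A fall from Phase 1 to Phase 2 could in part be habituation or a time trend, and a rise from Phase 2 to Phase 3 argues against a steady trend. A reader will want to see both contrasts, and rejecting both is where Bonferroni loses most relative to Holm. The sample is small and its size is not justified by a calculation, so avoidable loss of power deserves attention.

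**Working it through.** **Inputs from the documents.** n = 30, paired contrasts, m = 2 for pain. The sample size comes with no calculation, so there is no planned power figure to reproduce.

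**Assumed inputs.** Two-sided alpha 0.05; no dropout; paired t-tests; dz (mean paired difference divided by its SD) from 0.3 to 1.0. The two pain contrasts share Phase 2. With equal variances and equal between-phase correlation r, their covariance is σ²(1−r) and each has variance 2σ²(1−r), so they correlate at 0.5 whatever r is. The range 0 to 0.8 was also tried.

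**Rules for the two pain p-values.**
- Bonferroni rejects both if both p ≤ 0.05/2 = 0.025.
- Holm rejects both if the smaller p ≤ 0.025 and the larger p ≤ 0.05.
- Each rejects at least one if the smaller p ≤ 0.025, so that chance is the same under both.

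**One contrast at a fixed threshold.** Power is that of a noncentral t with 29 df and noncentrality dz√30. At dz 0.6 the noncentrality is 0.6 × 5.477 = 3.29, and power is 81.6% at 0.025 against 88.8% at 0.05. For 80% power, dz must be 0.589 at 0.025 and 0.529 at 0.05.

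**Family-wise error (simulation, 100,000 trials per scenario).** With both nulls true it is 4.8% for both methods at contrast correlation 0 or 0.5. With one true effect (dz 0.6) and one null, the null contrast is rejected in 2.4% of trials under Bonferroni and 4.4% under Holm, still below 5%.

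**Power to reject both pain contrasts, equal effects, contrast correlation 0.5.**

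| dz | Bonferroni | Holm | Gain (points) |
|---|---|---|---|
| 0.3 | 11.7% | 18.3% | 6.6 |
| 0.4 | 27.5% | 38.0% | 10.5 |
| 0.5 | 48.9% | 61.0% | 12.1 |
| 0.6 | 70.7% | 80.5% | 9.8 |
| 0.7 | 86.5% | 92.3% | 5.8 |
| 0.8 | 95.3% | 97.8% | about 2.5 |
| 1.0 | 99.7% | 99.9% | 0.2 |

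Over contrast correlations 0 to 0.8, the gain at dz 0.4 to 0.6 is about 8 to 14 points. Requiring a significant ANOVA first hardly changes it (9.7 points at dz 0.6). With unequal effects at correlation 0.5, the gain is 12.1 points for dz 0.6 and 0.4, and 10.8 for dz 0.8 and 0.5.

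**Power for the fall alone (Phase 1 versus Phase 2), contrast correlation 0.5.**

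| dz of fall | dz of return | Bonferroni | Holm | Gain (points) |
|---|---|---|---|---|
| 0.5 | 0 | 64.8% | 64.9% | 0.1 |
| 0.5 | 0.2 | 64.8% | 65.3% | 0.5 |
| 0.5 | 0.3 | 64.8% | 66.4% | 1.6 |
| 0.5 | 0.5 | 64.8% | 70.8% | 6.0 |
| 0.6 | 0.4 | 81.9% | 83.5% | 1.6 |
| 0.6 | 0.6 | 81.7% | 86.6% | 4.9 |

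At the edge case of zero contrast correlation, with equal effects of dz 0.5, the gain is 71.7 − 64.8 = 6.9 points.

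**HR and BP, if all six pairs are tested.** Bonferroni uses 0.05/6 = 0.0083 throughout. Holm uses 0.0083, 0.010, 0.0125, 0.0167, 0.025 and 0.05 in turn. For Phase 1 versus Phase 2 at dz 0.6, power is 0.67 to 0.68 under Bonferroni and 0.70 to 0.78 under Holm, a gain of about 3 to 10 points. It depends on how far drilling shifts the parameter from baseline and on whether it returns in Phase 3. Family-wise error among the drilling phases is 2.2% to 2.4% for Bonferroni and at most 4.5% for Holm.

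**The case against.** The strongest reply is that nothing here is wrong. Bonferroni is prespecified, valid and conservative, no conclusion becomes misleading, and the chance of at least one pain rejection is identical under Holm. That stands: this is an efficiency gain, not the correction of an error.

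A reader might infer that Bonferroni costs this trial about 10 points of power. The documents do not support that as a general figure, for three reasons.
- It needs moderate effects. No effect size is stated, and the gain nearly vanishes from dz 0.8 upward.
- It needs a rule that both pain contrasts must be significant, and neither section I nor VI-3 contains one. For the fall alone, the gain is under 1 point when pain returns weakly or not at all. It reaches 5 to 6 points only when pain returns about as strongly as it fell. Only 120 seconds separate the end of the music from Phase 3, so an equal return cannot be taken for granted.
- It does not carry over to HR and BP, where the pairs are not even listed.

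The both-contrasts argument also cuts against Holm. If both rejections were formally required for one joint claim, each could be tested at 0.05 without adjustment: 81.3% at dz 0.6, against 80.5% with Holm. But the plan sets no such rule and keeps a family-wise adjustment. Holm is the smallest change consistent with that.

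Two further points stand. Holm lacks simple matching simultaneous confidence intervals, which is a real drawback with 30 patients. And section V describes the study in the past tense, as conducted from October to December 2025, so changing to a method that can only add significant results is not a mere edit.

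**Conclusion.** The point holds as a cheap improvement. For the pain pairs and for the pairs within HR, systolic BP and diastolic BP, Holm gives the same family-wise guarantee as the planned method and never rejects less. That part needs no assumption about the data.

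The size does need assumptions: n = 30, two-sided 0.05, normal paired differences, and the effects and correlations shown above. On these, the gain is about 0 to 14 points for showing both pain contrasts and about 0 to 6 for the stated hypothesis (just under 7 at zero contrast correlation). For Phase 1 versus Phase 2 in HR or BP it is about 3 to 10 points at dz 0.6, if six pairs are tested. If the Friedman route is taken, the Holm rule still applies to paired rank tests, but these power figures are for t-tests.

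The documents support neither a fixed loss of 10 points nor a requirement that pain must be shown both to fall and to return.

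**What to change.** In VI-3, replace the Bonferroni wording by 'Holm step-down adjustment' in two places: for the pain pairs, and for the pairs within each of HR, systolic BP and diastolic BP. Use paired t or Wilcoxon p-values as inputs, and apply the rule to whatever set of pairs the final SAP keeps.

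Make the change by a dated amendment before outcome data are examined. The documents do not say whether that has already happened. If it has, keep Bonferroni as the planned analysis and report Holm as a labelled sensitivity analysis.

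The cost is a short wording change, the amendment record and one argument in the Python code. Because Holm has no simple matching simultaneous intervals, report ordinary or Bonferroni confidence intervals beside the Holm p-values and say which they are.

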- Nocturne Op.9 No.2 in Eb Major – Chopin
- Cello Suite No. 1 in G Major, BWV 1007: I. Prélude in C Major – Bach

- Sonata for Two Pianos K.448: II. Andante in D Major – Mozart
- Clair de Lune in Db Major – Debussy

IV- Type of Dental Procedure Studied

The experimental situation selected for this study is dental drilling during cavity treatment, performed without local anesthesia or in conditions where pharmacological analgesia is partially or totally ineffective.

- **Stimulus:** Dental drilling constitutes a continuous painful stimulus associated with the activation of pain responses and the autonomic nervous system.
- **Scientific Model:** It represents a relevant model for studying central mechanisms of pain modulation (Melzack & Wall, 1965b; Tracey & Mantyh, 2007).
- **Clinical Relevance:** While local anesthesia is standard, it can be ineffective during acute pulp inflammation, in patients with hypersensitivity/intolerance to anesthetics, or due to complex nerve anatomy (Hargreaves & Keiser, 2002; Meechan, 2005).
- **Patient Preference:** Some patients prefer to tolerate the pain of drilling rather than experience the prolonged jaw numbness associated with local injections.
- **Alternative:** In these situations, functional music therapy serves as a pertinent non-drug analgesic alternative. Music is a non-invasive intervention that can modulate perceived pain, anxiety, and autonomic activation through attentional, emotional, and autonomous mechanisms (Bradt et al., 2013; Roy et al., 2008).

V- Methodology

The study was conducted from October 1, 2025, to December 23, 2025, in a private dental clinic in Aley, Mount Lebanon, following ethical approval from Antonine University on July 16, 2025.

V-1- Population

- **Inclusion Criteria:** Adult patients (ages 18–60) visiting the clinic for cavity treatment who provide informed consent.
- **Exclusion Criteria:** Non-consenting patients, children, patients with mental or physical disorders, pregnant women, and patients taking analgesics, anxiolytics, or antidepressants.

V-2- Study Procedure

1. **Welcome:** The patient is welcomed in a calm atmosphere and the procedure is explained.
2. **Assessment:** The patient completes a general information questionnaire and the Corah Dental Anxiety Scale (DAS).

3. **Consent & Selection:** The patient signs the informed consent form, chooses their musical sequence, and adjusts the volume.

On the dental chair :

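### The four-phase HR/BP ANOVA mixes rest versus drilling with music versus no music, and the HR/BP pairwise comparisons are not named

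*Combined protocol and SAP*

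**What the plan says.** Section VI-1 describes a "Single-arm, within-subject experimental study" with "30 adults undergoing dental treatment for caries" and lists its phases as "Baseline (T0), Phase 1 (pre-music silence), Phase 2 (music), Phase 3 (post-music silence". Section V-2 gives the conditions. At baseline, "Heart rate (HR) and blood pressure (BP) are measured at rest (T0"; Phase 1 is "30 seconds of drilling without music"; Phase 2 is drilling with music; Phase 3 is drilling after the music has ended. Pain is scored at T1, T2 and T3 only.

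For HR, systolic BP and diastolic BP, section VI-3 plans "Repeated measures ANOVA for HR, systolic BP, and diastolic BP across the four phases", followed by "Pairwise comparisons with Bonferroni correction". No pairs are listed there. For pain, the same section names two: Phase 1 vs Phase 2 and Phase 2 vs Phase 3.

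Section IV describes the drilling stimulus as "associated with the activation of pain responses and the autonomic nervous system". The documents give no alpha, sidedness, effect size, SD or power calculation, and do not say whether the Bonferroni correction also spans the three physiological outcomes.

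**The concern.** Research question 2 asks whether music modulates autonomic activity. The phase factor in the HR/BP ANOVA has four levels that differ in two ways: T0 differs from the rest by the absence of drilling, and T2 differs from T1 and T3 by the presence of music. The protocol itself expects drilling to activate the autonomic nervous system, so it expects T0 to differ from the other phases whether or not music does anything. A report that HR or BP changed significantly across phases could then be read as support for music when it shows only that drilling is stressful.

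The pairwise step is where music can be separated from drilling, but its family is left open. An analyst could correct over two, three or six pairs, and the choice changes the power of the comparisons that matter.

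**Working it through.** The plan has no figure of its own to reproduce, so the check uses stated assumptions.

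**Inputs.** From the documents: n = 30, four phases, T0 at rest, T1-T3 with drilling. Assumed: two-sided 0.05 per outcome, SD of 1 at each phase, and a common within-person correlation ρ of 0.5, 0.6 or 0.7 (so sphericity holds). The drilling shift d (0.3 or 0.5 SD) and music effect δ (0.5 SD) are also assumed.

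**Step 1: four-phase omnibus test with no music effect.** The phase means are (−d, 0, 0, 0), so the sum of squared deviations from their mean is (3/4)d². The noncentrality is λ = n × (3/4)d² / (1 − ρ), with 3 and 87 degrees of freedom.

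- d = 0.3: 30 × 0.0675 = 2.025. Dividing by 0.5, 0.4 and 0.3 gives λ = 4.05, 5.06 and 6.75. Rejection probability: 35%, 43% and 55%.
- d = 0.5: 30 × 0.1875 = 5.625, giving λ = 11.25, 14.06 and 18.75. Rejection probability: 79%, 88% and 96%.
- d = 0: 5%.

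Simulation with the Greenhouse-Geisser correction (20,000 trials per scenario) gives slightly lower values: 33/41/53% at d = 0.3 and 78/87/95% at d = 0.5.

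**Step 2: the same test on T1-T3.** With no music effect and no trend over time, the three means are equal, λ = 0, and the test rejects 5% of the time whatever the size of d.

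**Step 3: the pairs.** Four phases give 4 × 3 / 2 = 6 pairs. Three involve T0, one (T1 vs T3) compares the two controls, and two (T1 vs T2, T2 vs T3) set music against a drilling control. The per-pair alpha is 0.05/6 = 0.0083 for six pairs and 0.05/2 = 0.025 for two.

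**Step 4: power for T1 vs T2.** The standardized paired difference is dz = δ / √(2(1 − ρ)). At δ = 0.5 this is 0.50, 0.56 and 0.65. Noncentral t with 29 degrees of freedom and noncentrality dz × √30 gives:

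| ρ | 0.05/6 | 0.05/2 | Loss (points) |
|---|---|---|---|
| 0.5 | 47% | 65% | 17 |
| 0.6 | 59% | 75% | 16 |
| 0.7 | 75% | 87% | 12 |

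Losses are taken before rounding. Simulation gives 48/60/75% for the 0.05/6 column.

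**Step 5: false positives in the music pairs.** In simulation with no music effect and drilling shifts of 0.5 and 0.8 SD, at least one of the two music pairs was significant at 0.05/6 in 1.4-1.7% of trials. At 0.05/2 the figure was 4.7% (shift of 0.8 SDs of the paired difference). Neither exceeds 5%.

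**The case against.** The strongest reply is that the plan does not stop at the omnibus test. Pairwise comparisons follow, they can separate music from drilling, and nothing in the SAP says that a significant phase effect will be read as a music effect. That stands, and step 5 confirms that the music pairs keep their error rate. It does not settle the matter, because the pairs are unnamed and no text tells the reader to set the omnibus result aside when judging music.

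A reader might infer several stronger things that the documents do not support:

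- *That the four-phase test cannot see music.* It responds to any phase difference. With no drilling effect and a music effect of dz 0.5, it rejects 79% of the time, as does the three-phase test. It is non-specific, not insensitive.
- *That six pairs are planned.* Six is the default reading of an unrestricted pairwise step over four phases, but the two-pair rule for pain stands just above it. The text leaves the family unspecified.
- *That the T0 pairs are irrelevant.* T0 vs T1 shows whether drilling provoked a response, and T0 vs T2 bears on whether it persisted under music. Neither isolates music, but both help interpretation.
- *That the power lost is the gap between about 48-75% and the 86-98% obtained from T2 − (T1+T3)/2 at 0.05.* That comparison mixes a looser alpha with a more efficient contrast. Going from six pairs to two accounts for 12-17 points.

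The size of the drilling shift is also unknown. If resting values in the chair are already raised by anticipation, d could be small and the omnibus problem smaller.

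**Conclusion.** The concern holds in a limited form. The four-phase HR/BP omnibus test is not evidence for research question 2: with no music effect it would be significant in about 35-55% of trials at a 0.3 SD drilling shift and 79-96% at 0.5 SD. Separately, the HR/BP pairwise family is unspecified. On the six-pair reading, power for T1 vs T2 at a 0.5 SD music effect falls from 65-87% to about 47-75%. All these figures rest on the assumed alpha, correlations and effect sizes.

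Only secondary outcomes are affected. Pain has no T0 score and its pairs are named, so a reader should not infer that the primary conclusion is at risk, or that the planned HR/BP music pairs would yield excess false positives. This is a should-fix point.

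**What to change.** In section VI-3, for HR, systolic BP and diastolic BP:

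1. Run the omnibus test on T1, T2 and T3 only.
2. Name T1 vs T2 and T2 vs T3 as the music contrasts, with Bonferroni over those two, as for pain. State whether the correction applies within each outcome or across all three. Report mean differences with 95% confidence intervals.
3. Report T0 comparisons, such as T1 − T0, separately as a check that drilling provoked a response.
4. State that no four-phase omnibus result will be used to support a claim about music.

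The contrast T2 − (T1+T3)/2 may be added as supportive. It should not replace the named pairs, because it assumes no carryover of music into T3 after the 120-second pause. If the music effect carried over fully, its expected value would be halved (δ − δ/2), while T1 vs T2 would be unaffected.

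No new data are needed. The cost is that T0 comparisons become descriptive. Section V also describes the study as already conducted, to December 23, 2025, so the change must be dated and disclosed as made after that period.
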